5.2 APPENDIX 2 CHANGES TO PROTOCOL-PLANNED ANALYSES

This Statistical Analysis Plan (SAP) for study EFC16461 Study C is based on the protocol dated 17 March 2022 (amended protocol 5). This section summarizes major statistical changes in the protocol amendment(s) relevant to Study C.

The primary purpose of Amended protocol 5 was to conduct a Study C with a study population and design similar to the completed Study A, to meet Health Authority requirements to provide data from two adequate and well-controlled clinical trials to support filing of a marketing application.

Table 8 - Major statistical changes in protocol amendment(s)

| Amendment Number | Date Approved | Rationale | Description of statistical changes |
|------------------|---------------|---|---|
| 5 | 17-Mar-2022 | Add Study C with similar design to Study A to meet Health Authority requirements. | Study C is added with similar design and patient population as Study A. Study C is also stratified in adults by presence of angioedema. |

5.3 APPENDIX 3 DEMOGRAPHICS AND BASELINE CHARACTERISTICS, PRIOR OR CONCOMITANT MEDICATIONS

Demographics, baseline characteristics, medical surgical history

The following demographics and baseline characteristics, medical and surgical history and disease characteristics at baseline will be summarized using descriptive statistics in the randomized population.

Demographic variables are:

- Age in years (quantitative and qualitative variable: < 12, 12- <18, 18- <40, 40 - <65, 65 - <75 and \geq 75 years),
- Gender (Male, Female),
- Race (White, Black or African American, Asian, American Indian or Alaska Native, Native Hawaiian or other Pacific Island, unknown),
- Ethnicity (Hispanic or Latino, Not Hispanic or Latino, Unknown),
- Region (**Asia**: China, Japan; **Latin America**: Argentina; **Western Countries**: Canada, USA, France, Germany, Spain **East Europe**: Hungary),
- Territory (**North America**: Canada, USA; **European Union**: France, Germany, Spain, Hungary; **Rest of World**: China, Japan, Argentina),
- Weight in kg (quantitative and qualitative variable: <60, \geq 60 kg),
- BMI in kg/m² (quantitative and qualitative variable: <30, \geq 30 kg/m²).

Baseline safety and efficacy parameters (apart from those listed above) will be presented along with the safety and efficacy summaries.

Medical (or surgical) history includes all the relevant medical (or surgical) history during the lifetime of the participant.

This information will be coded using the version of MedDRA currently in effect at Sanofi at the time of database lock.

Comorbidity will be summarized separately. The following comorbid diseases will be summarized from electronic case report form (eCRF) pages which were filled in by investigators based on participant reporting. Angioedema history will be further summarized under disease characteristics at baseline.

CSU history (Yes, Ongoing condition)

Angioedema (Yes, Ongoing condition)

Atopic Dermatitis (Yes, Ongoing condition)

Allergic rhinitis (Yes, Ongoing condition)

Allergic Conjunctivitis (Yes, Ongoing condition)

Asthma (Yes, Ongoing condition)

Food allergy (Yes, Ongoing condition)

Chronic Rhinosinusitis (Yes, Ongoing condition)

Nasal Polyps (Yes, Ongoing condition)

Eosinophilic Esophagitis (Yes, Ongoing condition)

Disease characteristics at baseline

The following baseline disease characteristics will be summarized by intervention group:

- Age at onset of CSU (years)
- Time since first diagnosis of CSU (years) to be derived as
(Year of randomization – Year of first diagnosis of CSU) + (month of randomization-month of first diagnosis of CSU)/12
- Presence of angioedema at baseline
 - Number of episodes in past 6 months
 - Time since last episode (months)
- Baseline ISS7 score (quantitative and qualitative variable: <13, \geq 13)
- Baseline UAS7 score (quantitative and qualitative variable: <28, \geq 28)
- Baseline weekly hives severity score (HSS7)
- Baseline angioedema activity score over 7 days (AAS7) for participants with angioedema
- Baseline urticaria control test (UCT)
- Baseline Dermatology Life Quality Index (DLQI)/Children's Dermatology Life Quality Index (CDLQI)
- Baseline Patient Global Impression of Severity (PGIS)
- Frequency of alcohol drinking in the past 12 months (never, occasional, at least monthly, at least weekly, at least daily) and number of drinks on a typical day (1 or 2, >2)
- Baseline IgE (quantitative and qualitative variable: <100 vs \geq 100)
- Baseline H1-AH dose (1-fold, 2-3-fold, 4-fold)

Prior or concomitant medications

All medications taken within 1 month before screening and until the end of the study, including all prior medications taken for CSU are to be reported in the case report form pages.

All medications will be coded using the World Health Organization-Drug Dictionary (WHO-DD) using the version currently in effect at Sanofi at the time of database lock.

- Prior medications are those the participant used prior to first investigational medicinal product (IMP) injection. Prior medications can be discontinued before first administration or can be ongoing during treatment phase.
- Concomitant medications are any interventions received by the participant concomitantly to the IMP, from first administration of IMP to last IMP intake + 98 days.
- Post-treatment medications are those the participant took in the period running from the end of the concomitant medications period up to the end of the study.
- A given medication can be classified as a prior medication and/or as a concomitant medication and/or as post-treatment medication. If it cannot be determined whether a given medication was taken prior or concomitantly or post, it will be considered as prior, concomitant, and post-treatment medication.

The prior and concomitant medications will be summarized for the randomized population.

Medications will be summarized by intervention group according to the WHO-DD dictionary, considering the first digit of the anatomic category (ATC) class (anatomic category) and the first 3 digits of the ATC class (therapeutic category). All ATC codes corresponding to a medication will be summarized, and participants will be counted once in each ATC category (anatomic or therapeutic) linked to the medication. Therefore, participants may be counted several times for the same medication.

Prior medications will be summarized separating for those taken for CSU versus other reasons. The tables for prior medications will be sorted by decreasing frequency of ATC followed by all other therapeutic classes based on the overall incidence across intervention groups. In case of equal frequency regarding ATCs (anatomic or therapeutic categories), alphabetical order will be used.

Concomitant medication received during first IMP to last IMP +14 days and concomitant medication received during first IMP to last IMP +98 days will be summarized separately. The tables for concomitant medications will be sorted by decreasing frequency of ATC followed by all other therapeutic classes based on the incidence in the dupilumab group. In case of equal frequency regarding ATCs (anatomic or therapeutic categories), alphabetical order will be used.

Medications will also be summarized by generic name sorted by decreasing frequency based on the incidence in the dupilumab group.

Rescue medications

The following rescue medications may be used:

- Additional doses of H1-AH up to 4-fold the recommended dose (2-fold in Japan).
- Short course of OCS.

The use of rescue medications should be delayed, if possible, for at least 8 weeks following the initiation of IMP. The following specific medications will be summarized:

- Rescue medications taken during the study will be summarized separately overall and by type (additional doses of H1-AH medications, OCS therapy).
- The total number of days rescue medication was taken by type will be summarized.

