### 1.3 SCHEDULE OF ACTIVITIES (SOA)

Procedures	Screening (2 to 4 weeks before Day 1)	Intervention period (Weeks)			Follow-up (12 weeks)	Notes
		0 (Day 1)	12	24		
Visit	1	2 a	3	4 (EOT) b	5 (EOS)	
Screening/baseline:						
Informed consent	X					
Medical history	X					
Prior and concomitant medication	X	X	X	X	X	Concomitant medication including rescue OCS taken since last visit will be collected throughout the study
Demographics	X					
Inclusion/exclusion criteria	X	X				
Patient e-diary training	X	X				
Randomization		X				
Study intervention						
Call IVRS/IWRS	X	X	X	X	X	
IMP administration			X c			IMP will be administered every other week except (for study A and study C) for children <30 kg and ≥15 kg where it will be administered every 4 weeks. The planned last dose is at Week 22 except (for study A and study C) for children <30 kg and ≥15 kg where it will be administered at Week 20. Participants (or their care givers) are allowed to perform IMP injections at home.
Dispense/Upload electronic diary d	X		X			Device is dispensed at Screening (including instructions for use). At the EOS, the e-diary is returned to the site.
Safetye						
Physical examination f	X	X		X	X	
Vital signs g	X	X	X	X	X	
Electrocardiogram (12 lead)	X			X		ECG to be locally collected and read

Procedures	Screening (2 to 4 weeks before Day 1)	Intervention period (Weeks)			Follow-up (12 weeks)	Notes
		0 (Day 1)	12	24		
Visit	1	2 a	3	4 (EOT) b	5 (EOS)	
Hematology, biochemistry, urine analysis h	X	X	X	X	X	
Hepatitis, HIV Serology, TB test i	X					
Pregnancy test j	Serum	Ur	Ur	Ur	Ur	In between visit urine pregnancy tests must be performed at home (Weeks 4, 8, 16, 20, 28, and 32)
AE reporting, including SAEs	X	X	X	X	X	
Pharmacokinetics and ADAe						
Serum PK samples for dupilumab concentration k		X	X	X	X	
Anti-dupilumab antibody k		X	X	X	X	
Biomarkerse						
Serum total IgE		X	X	X	X	
Basophil activation test (optional sub-study)		X	X	X		For participants (except pediatric participants in Studies A and B and all Study C participants) who decide to participate and provide consent for the optional basophil activation test.

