Medications will be summarized by intervention group according to the WHO-DD dictionary, considering the first digit of the anatomic category (ATC) class (anatomic category) and the first 3 digits of the ATC class (therapeutic category). All ATC codes corresponding to a medication will be summarized, and participants will be counted once in each ATC category (anatomic or therapeutic) linked to the medication. Therefore, participants may be counted several times for the same medication.

Prior medications will be summarized separating for those taken for CSU versus other reasons. The tables for prior medications will be sorted by decreasing frequency of ATC followed by all other therapeutic classes based on the overall incidence across intervention groups. In case of equal frequency regarding ATCs (anatomic or therapeutic categories), alphabetical order will be used.

Concomitant medication received during first IMP to last IMP +14 days (+28 days for children <30 kg) and concomitant medication received during first IMP to last IMP +98 days will be summarized separately. The tables for concomitant medications will be sorted by decreasing frequency of ATC followed by all other therapeutic classes based on the incidence in the dupilumab group. In case of equal frequency regarding ATCs (anatomic or therapeutic categories), alphabetical order will be used.

Medications will also be summarized by generic name sorted by decreasing frequency based on the incidence in the dupilumab group.

Rescue medications

The following rescue medications may be used:

- Additional doses of H1-AH up to 4-fold the recommended dose (2-fold in Japan)
- Short course of OCS

The use of rescue medications should be delayed, if possible, for at least 8 weeks following the initiation of IMP. The following specific medications will be summarized:

- Rescue medications taken during the study will be summarized separately overall and by type (additional doses of H1-AH medications, OCS therapy).
- The total number of days rescue medication was taken by type will be summarized.

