1 INTRODUCTION

1.1 STUDY DESIGN

This is a master protocol composed of 3 studies of similar design, 2 studies in participants who are omalizumab naïve (Study A and Study C) and 1 study in participants who are omalizumab intolerant or incomplete responders (Study B). Study A and Study C will include adults, adolescents (≥ 12 to < 18 years) and children (≥ 6 to < 12 years). Study B will include adults and adolescents. The three studies are 24-week, double-blind, randomized, placebo-controlled studies to evaluate the use of dupilumab in participants with chronic spontaneous urticaria (CSU) who remain symptomatic despite the use of H1-antihistamines (H1-AH).

After a screening period of 2 to 4 weeks, participants are centrally randomized (using permuted block randomization schedule) via interactive response technology (IRT) in a 1:1 randomization ratio to dupilumab (300 mg q2w for adults and adolescents ≥ 60 kg after a loading dose of 600 mg on Day 1; 200 mg q2w for adolescents < 60 kg and children ≥ 30 kg after a loading dose of 400 mg on Day 1; or 300 mg q4w for children < 30 kg and ≥ 15 kg after a loading dose of 600 mg on Day 1) or placebo over a 24-week treatment period. Randomization is stratified first by age (adults versus adolescents versus children in Study A and Study C, adults versus adolescents in Study B; up to approximately 5% of total sample size for children and approximately 5% of total sample size for adolescents). In adults, randomization is stratified further by country (Studies A, B, and C) and presence of angioedema at baseline (Study C only). In adolescents/children ≥ 6 to < 12 years of age, randomization is not stratified further.

The total anticipated number of participants across the 3 studies is approximately 384 randomized participants (130 participants in Study A, 104 participants in Study B and 150 participants in Study C).

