4 STATISTICAL ANALYSES

4.1 GENERAL CONSIDERATIONS

This SAP provides a comprehensive and detailed description of strategy and statistical techniques for the summary and analysis of EFC16461 Study C (omalizumab naïve) only. Study A (omalizumab naïve) and Study B (omalizumab intolerant or incomplete responders) were summarized separately in different SAPs.

In general, continuous data will be summarized using the number of observations available, mean, standard deviation (SD), median, minimum, and maximum. Categorical and ordinal data will be summarized using the count and percentage of participants.

The baseline value of efficacy parameters is defined as the last available value up to randomization date and prior to the first dose of study medication unless otherwise specified. The baseline value of the other parameters is defined as the last available value prior to the first dose of investigational medicinal product (IMP) if the participant is treated, or the last available value up to randomization date if the participant is not exposed to IMP.

Observation period

The observation period will be divided into 4 segments:

- The **pre-treatment period** is defined as the period up to first IMP administration.
- The **treatment-emergent (TE) period** is defined as the period from the first IMP administration to the last IMP administration + 98 days. The treatment-emergent period includes the following 2 periods:
 - The **on-treatment period** is defined as the period from the first IMP administration to the last administration of the IMP + 14 days (+28 days for children <30 kg)
 - The **residual treatment period** is defined as the period from the end of the on-treatment period to the end of the treatment-emergent period.
- The **post-treatment period** is defined as the period from the end of the treatment-emergent period.

The on-study observation period is defined as the time from start of intervention until the end of the study defined as the status date collected on e-CRF page “Completion of End of Study”.

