4.7.1 Extent of exposure

The extent of IMP exposure will be assessed by the duration of IMP exposure and compliance and summarized within the safety population.

Duration of IMP exposure

Duration of IMP exposure is defined as last dose date – first dose date + 15 days (or +29 days for children < 30 kg), regardless of unplanned intermittent discontinuations. If the date of the last dose of IMP is missing, the duration of IMP will be left as missing.

Duration of IMP exposure will be summarized descriptively as a quantitative variable (number, mean, SD, median, minimum, and maximum). In addition, duration of IMP exposure will also be summarized categorically by numbers and percentages for each of the following categories and cumulatively according to these categories:

- >0 and \leq 2 weeks
- >2 and \leq 4 weeks
- >4 and \leq 8 weeks
- >8 and \leq 12 weeks
- >12 and \leq 16 weeks
- >16 and \leq 20 weeks
- >20 and \leq 24 weeks
- >24 weeks and \leq 24 weeks + 3 days
- >24 weeks + 3 days

Additionally, the cumulative duration of IMP exposure will be provided, defined as the sum of the duration of treatment exposure for all participants, and will be expressed in participant years.

Treatment compliance

A given administration will be considered noncompliant if the participant did not take the planned dose as required by the protocol. No imputation will be made for participants with missing or incomplete data.

Percentage of treatment compliance for a participant will be defined as the number of administrations that the participant was compliant divided by the total number of administrations that the participant was planned to take from the first administration of IMP up to the actual last administration of IMP.

Treatment compliance will be summarized quantitatively and categorically: <80%, \geq 80%.

Cases of overdose (defined as at least twice the intended dose during an interval of less than 11 days (or less than 25 days for children < 30 kg) will be summarized.

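### The shorter concomitant-medication table in the Study C SAP ends at last dose +14 days for everyone, without the +28-day extension that the same SAP gives children under 30 kg elsewhere

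*SAP*

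**What the plan says.** Study C enrols children. Section 1.1 of its SAP states "Study A and Study C will include adults, adolescents" and then children aged 6 to under 12, planned at up to about 5% of the sample, and gives "150 participants in Study C" as the planned size. Those weighing 15 to under 30 kg have their own regimen, "300 mg q4w for children" in that weight band. In the protocol's Schedule of Activities (1.3), the planned last dose is Week 22, except for this group, "where it will be administered at Week 20".

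The Study C SAP adapts its interval-based rules to this regimen in three places:

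- Section 4.1 runs the on-treatment period from first IMP "to the last administration of the IMP + 14 days (+28 days for children <30 kg", closing the bracket there.
- Section 4.7.1 adds 15 days to the span from first to last dose to obtain exposure duration, or 29 days for children under 30 kg, "regardless of unplanned intermittent discontinuations".
- Section 4.7.1 also widens the overdose interval for these children, from under 11 to under 25 days.

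Section 5.3 (Appendix 3) does not. It summarizes separately "Concomitant medication received during first IMP to last IMP +14 days and concomitant medication received during first IMP to last IMP +98 days". The same sentence in the Study A SAP (5.3) begins "Concomitant medication received during first IMP to last IMP +14 days (+28 days for children <30 kg" and closes the bracket before going on to the +98-day table.

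**The concern.** The windows of +14 and +98 days in section 5.3 coincide with the ends of the on-treatment and treatment-emergent periods in section 4.1. The first table therefore reads as the on-treatment medication table. If so, it applies the every-2-weeks interval to children dosed every 4 weeks and stops 14 days before their on-treatment period ends.

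The omission looks inadvertent. The Study C sentence is word for word that of the Study B SAP. Study B enrols no children and has a plain +14-day on-treatment period, so the wording is correct there. The Study C SAP shows other signs of carry-over: its tipping-point analysis (4.3.3) keeps stopping thresholds for an interim and a final analysis (0.021 and 0.043), which are the Study B levels, although section 4.9 plans no interim analysis.

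At stake is consistency within one descriptive display. On the same days, a child would count as exposed and have on-treatment laboratory and vital-sign values, yet a newly started medication would be missing from the matching table. Studies A and C, the two trials in omalizumab-naïve patients, would also use different windows for the same dosing group.

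**Working it through.** The plan gives no calculated figure to reproduce. The check compares window ends by day count.

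**Inputs**
- Planned last dose: Week 22, or Week 20 for children under 30 kg (protocol 1.3).
- Day numbering: Week w falls on Day 7w + 1, as in the target days of the Study C SAP (5.4): Week 20 = Day 141, Week 22 = Day 155, Week 24 = Day 169.
- Shorter medication window: last dose + 14 for all (Study C SAP 5.3).
- On-treatment period: last dose + 14, or + 28 for children under 30 kg (Study C SAP 4.1).
- Exposure duration: last dose − first dose + 15, or + 29 for these children (Study C SAP 4.7.1).

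**Window ends under the planned schedule**

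| Group | Last dose | Shorter medication table ends | On-treatment period ends | Exposure duration |
|---|---|---|---|---|
| Dosed every 2 weeks | Day 155 | 155 + 14 = Day 169 | 155 + 14 = Day 169 | 155 − 1 + 15 = 169 days |
| Children under 30 kg, every 4 weeks | Day 141 | 141 + 14 = Day 155 | 141 + 28 = Day 169 | 141 − 1 + 29 = 169 days |

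For participants dosed every 2 weeks, the table and the on-treatment period end together. For children under 30 kg they differ by 169 − 155 = 14 days, Days 156 to 169. These are the Week 23 and Week 24 diary weeks (156–162 and 163–169). If such a child stops treatment early, the same 14-day gap follows the actual last dose.

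**After the fix**
With +28 days, the table for these children ends on 141 + 28 = Day 169, in line with their on-treatment period and with the other participants.

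**Number of children**
The cap for children of any weight is 5% × 150 = 7.5, so about 7 to 8. Only those under 30 kg are affected, and the documents do not give their share. Study A enrolled 2 children among 138 participants (protocol 2.1), weights not stated. At that rate Study C would have 2/138 × 150 ≈ 2.2 children.

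**Which analyses depend on these days**

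| Study C analysis | Window used | Affected |
|---|---|---|
| Shorter concomitant-medication table (5.3) | last dose + 14 | Yes |
| Longer concomitant-medication table (5.3) | last dose + 98 | No |
| Adverse events (4.1, 4.7.2) | treatment-emergent, last dose + 98 | No |
| PCSA for laboratory, vital signs, ECG (4.7.3.1) | treatment-emergent | No |
| Last and worst laboratory and vital-sign values (4.7.3.1) | on-treatment, with the +28-day extension | No, but out of step with the shorter table |
| Rescue medication overall and by type (5.3) | during the study | No |
| Antihistamine rescue; OCS dose and days (4.5.1) | planned treatment period, to Day 169 | No |
| Time to first OCS (4.4.2) | censored at Day 169 or earlier | No |
| Primary analysis (4.3.2) | medication start date, use up to Week 24 | No |

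**The case against.** The strongest reply is that nothing of consequence depends on this table. Several parts of that reply stand.

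- Section 5.3 never calls the +14-day table on-treatment. That is an inference from the matching windows in section 4.1 and from the Study A sentence. It is a reasonable one, since no reason is given for treating these children differently from Study A.
- The data are not lost. Section 5.3 defines concomitant medication as running to last dose +98 days, so a drug started on Days 156 to 169 appears in the longer table. A drug already in use by Day 155 is in both. Participants are counted once per ATC category, so a new drug in a class already counted changes no ATC count. The gap is 14 of 168 days (8.3%) for such a child, but that is not 8.3% of the information.

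A reader might go further and infer that adverse events on those days are out of step with the medication table. The documents do not support this: adverse events are classified by the treatment-emergent period, which ends at +98 days for everyone, and the +98-day table matches it.

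A reader might also infer that rescue or prohibited medication taken just before the Week 24 assessment goes unreported, or that the primary result is affected. Neither follows. Rescue medication has its own summaries, time to first selected prohibited or rescue medication is a separate analysis (4.5.1), and the primary analysis works from the medication start date without reference to this window.

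What the reply does not remove is the contradiction itself: one rule in the Study C SAP gives a different end day from the definitions it otherwise follows.

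**Conclusion.** The point holds as an internal inconsistency in one descriptive table. For children under 30 kg, the shorter Study C table ends 14 days before their on-treatment period, at Day 155 instead of Day 169 on the planned schedule. A medication first started in that interval is absent from this table only. Those days do count in exposure duration and in the last and worst on-treatment laboratory and vital-sign values.

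The size is small: at most about 7 to 8 children of any weight, fewer under 30 kg, and possibly none. No efficacy, adverse event, PCSA or rescue-medication result changes, and neither does any conclusion of the study.

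This rests on two assumptions: that the +14-day table is meant to cover the on-treatment period, and that the last dose is given on its planned day. The second fixes the calendar days; the 14-day gap does not depend on it.

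**What to change.** In section 5.3 of the Study C SAP, word the first window as the Study A SAP does: "Concomitant medication received during first IMP to last IMP +14 days (+28 days for children <30 kg", with the bracket closed, and leave the +98-day window as it stands. It would also help to call the first table on-treatment and refer to section 4.1, so that a single definition governs both.

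The cost is one phrase in the SAP and one condition in the table program. No new data are needed, and dosing and study conduct are not touched.
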